## SCHEMA

### Treatment of Brain Metastases from Breast Cancer with Eribulin Mesylate

#### Primary Objectives:

To determine the 3-month central nervous system (CNS)-progression free survival (PFS) for patients with metastatic breast cancer with brain metastases treated with eribulin mesylate.

C1D1	C1D8	C2D1	C2D8	C3D1	C3D8	C4D1	C4D8	C4D21
------	------	------	------	------	------	------	------	-------

= MRI

= Eribulin 1.4mg/m^2  
21 day cycles

## **1.0 INTRODUCTION**

### **1.1 Name of Study Disease/Stage: Breast cancer with brain metastases**

### **1.2 Name of Investigational Agent: Eribulin Mesylate**

#### **1.3 Clinical Data for Eribulin:**

Eribulin mesylate (Halaven®) is a microtubule inhibitor approved by FDA in metastatic breast cancer patients who have received at least two prior chemotherapy regimens for metastatic disease. Multiple phase 2 studies and one noteworthy phase 3 study have established the efficacy of eribulin mesylate (Halaven®) in patients with metastatic breast cancer (MBC) (1-4). The efficacy of eribulin mesylate has also been evaluated in other advanced solid tumors. These phase 2 studies have demonstrated that eribulin mesylate shows activity in patients with advanced non small cell lung cancer, prostate cancer, soft tissue sarcoma and platinum-susceptible ovarian, fallopian tube or peritoneal cancers. Eribulin mesylate was evaluated in a Phase 3, open label, randomized trial for patients with metastatic or locally recurrent breast cancer against the therapy of physician's choice (TPC) (4). Eribulin mesylate 1.4mg/m^2 was administered intravenously over 2-5 minutes on days 1 and 8 of 21 days cycles; the median duration of treatment was 3.9 months. TPC included chemotherapy (96% received single agent vinorelbine, gemcitabine, capecitabine, taxanes, or anthracyclines) or hormonal therapy. The median duration of treatment in the TPC arm was 2.1 months for chemotherapy and 1 month for hormonal therapy. Participants had either received, responded poorly or became refractory to at least 2 prior chemotherapy treatments including an anthracycline and taxane unless contraindicated either the adjuvant or metastatic setting. Overall, 16% of the patients had human epidermal growth factor receptor 2 (HER2)-positive disease and 19% were estrogen receptor (ER), progesterone receptor (PR) and HER2- negative (triple-negative). Although only 2 previous chemotherapy regimens were mandatory for enrollment, 9% of patients had received 4 or more chemotherapy regimens. For the 508 women treated with eribulin mesylate, the median overall survival (OS) was 13.1 months; the median OS was 10.6 months in 254 women in the TPC arm ( $p = 0.041$ ). A significantly higher overall response rate (ORR) was also found with eribulin mesylate compared to TPC (12% vs. 5%) ( $p = 0.002$ ). Further analysis of the study results suggested that survival benefit with eribulin mesylate was independent of age without resulting in additional toxicity in older patients. Hence, it was recommended that age alone should not preclude older patients from receiving the drug regimen (5). Overall, this study demonstrated that eribulin mesylate was an effective agent associated with survival benefit compared to other standard regimens in heavily pretreated patients with locally advanced breast cancer or MBC. This trial formed the basis for the 2010 United States Food and Drug Administration approval of eribulin mesylate for advanced breast cancer after two or more chemotherapy regimens.

#### **1.3.1 Clinical Pharmacokinetics of Eribulin:**

Eribulin mesylate when dosed at 1.4 mg/m^2 as an intravenous bolus has been shown to be well tolerated at 2 dosing schedules: on days 1 and 8 of 21-day cycles and on days 1, 8, and 15 of 28-day cycles in patients with MBC (1-4). Eribulin is a colorless, sterile solution for injection. Each vial contains 1 mg of eribulin as a 0.5-mg/mL solution in a 5:95 ratio of ethanol to water (6). Eribulin does not require pretreatment with corticosteroids or antihistamines (6) since its water solubility negates the requirement for a lipophilic vehicle such as polysorbate 80 (docetaxel) or

Cremophor (paclitaxel), which have the potential to cause a hypersensitivity reaction. Eribulin is freely soluble in water and various organic solvents including ethanol, benzyl alcohol, and dimethyl- sulfoxide (7). Eribulin vials should be stored at 25 degree Centigrade and should not be frozen (6). The pharmacokinetic profile of eribulin is linear and dose proportional. When administered intravenously, eribulin has a rapid and extensive volume of distribution, slow elimination phase, and biexponential plasma disposition (8-13). The mean plasma half-life of eribulin is approximately 37.8hours, which allows for prolonged drug exposure to exert the antimitotic action (11). Eribulin is eliminated primarily via the liver, where it is metabolized to 4 monooxygenated metabolites by CYP3A4. The CYP3A4-mediated biotransformation of eribulin is slow, which results in delayed hepatic clearance (14). A minor amount of eribulin (~7%) is renally excreted as the parent compound (10). Dose adjustments for patients with moderate renal impairment, with creatinine clearance between 30 and 50 mL/min, are recommended (17). In a clinical setting, eribulin presents an insignificant risk for drug-drug interactions with CYP3A4 inhibitors and inducers (17). Hepatic impairment decreases clearance and prolongs the elimination half-life of eribulin (15). Because of a significant risk of grade3/4 neutropenia, it is recommended to reduce the eribulin dose by half in patients with moderate hepatic impairment (16).

#### **1.4 Study Rationale**

Brain metastases occur in 20-40% of all cancer patients (18) and account for more than half of all intra-cranial tumors in adults with approximately 170,000 new cases diagnosed annually in the United States alone (19). Breast cancer represents the primary tumor in 15-20% of patients with brain metastases (19). The risk of developing brain metastases from breast cancer varies with the underlying biology of the disease (20), stage of the disease and effectiveness of systemic therapy. Among women with advanced breast cancer, the long term cumulative risk for developing brain metastases from breast cancer is estimated at 10- 15% (21). The 5 year cumulative incidence of brain metastases in triple negative breast cancer has been reported as 10% (22) but has been reported to be 46 % following the diagnosis of metastatic breast cancer (23). In HER-2 positive disease, the incidence may be up to 36% following the diagnosis of metastatic breast cancer (24, 25) and has been recently estimated as almost 50% based on data in long term follow up patients with both early and advanced HER-2 positive disease (26).

Brain metastases are associated with considerable morbidity and mortality. The most common presenting symptoms of brain metastases are headache, cognitive impairment and focal weakness, seizures and ataxia. Treatment of brain metastases are mainly palliative and typically include whole brain radiation therapy (WBRT), stereotactic surgery (SRS) or surgical resection. In patients with brain metastases from breast cancer the median survival depending on the subtype is 4-7.5 months (27) and median survival with SRS is 7-18 months (28, 29).

Currently there is no approved drug therapy for brain metastases from metastatic breast cancer. Conventional cytotoxic drugs penetrate the brain poorly and intracranial response rates are low and of short duration. Paclitaxel which has become a standard of care for breast cancer has very little penetration across the blood-brain barrier (20) and has not demonstrated efficacy against breast metastases to brain. Targeted therapies such as lapatinib have been tested in HER 2 positive metastatic breast cancer with a response rate of 3-6% (31). Furthermore, the use of cytotoxic drugs is limited by systemic toxicity; restrictions imposed by blood brain barrier and the chemo sensitivity of the primary tumor. Patient outcomes with brain metastases are poor. Median survival following development of

brain metastases from triple negative breast cancer is approximately 4 months with combine modality of WBRT with chemotherapy (22). Outcomes are generally better for patients with HER 2 positive brain metastases (32) but when progression after cranial irradiation occurs, outcomes are similarly poor even after administration of a combination of capecitabine plus lapatinib. Given the poor prognosis of patients with brain metastases and the lack of effective drug treatment options, there is a need for development of new therapeutic agents and technology to evaluate early response to these therapeutic agents.

Despite being approved in metastatic breast cancer treatment, eribulin mesylate's therapeutic effectiveness on brain metastases from breast cancer has not been studied in a prospective clinical study. Matsuoka and colleagues described a case of a woman with brain metastases from breast cancer who had a significant response in brain that persisted for 4 months when treated with eribulin mesylate (33).

Additionally two patients with brain metastases from breast cancer treated at University Hospitals Seidman Cancer Center showed marked response to eribulin. Based on these observations, we hypothesize that eribulin may have activity in patients with brain metastases from breast cancer.

We propose to study a clinically meaningful endpoint, the 3-month CNS-progression free survival (PFS), of eribulin mesylate in breast cancer patients with brain metastases.

## **2.0 OBJECTIVES**

### **2.1 Primary Objectives:**

To determine the 3-month central nervous system (CNS)-progression free survival (PFS) for patients with metastatic breast cancer with brain metastases treated with eribulin mesylate.

### **2.2 Secondary Objective(s):**

2.2.1 Estimate CNS complete and partial response rates (CR and PR) and duration of CNS response in this patient population.

2.2.2 Evaluate toxicity in patients with breast cancer with brain metastases treated with eribulin mesylate.

2.2.3 Estimate clinical benefit rate (CBR) at 3 months in breast cancer patients with brain metastases treated with eribulin mesylate. (CBR is the sum of CR, PR and stable disease at 3 months).

2.2.4 To estimate systemic disease (extra cranial) response rate and duration of systemic response in this patient population.

2.2.5 Overall survival in this patient population.

## **3.0 STUDY DESIGN**

### **3.1 Design:**

This is a phase II study that will require 20 patients to evaluate the primary objective (CNS PFS at 3 months). Study patients will have a baseline brain MRI and a second MRI at 12 weeks to evaluate disease.

**3.2 Number of Subjects:** A total of 20 evaluable patients will be required for the study:

**3.3 Expected Duration of Subject Participation:** Death or disease progression or toxicity.

### **3.4. Duration of Therapy**

In the absence of treatment delays due to adverse events, treatment may continue on study until one of the following criteria applies:

- Systemic or CNS disease progression,
- Intercurrent illness that prevents further administration of treatment,
- The investigator considers it, for safety reasons, to be in the best interest of the patient.
- Unacceptable treatment related toxicity, NCI CTC AE version 4.0. Grade 3 or 4 that fails to recover to baseline or < Grade 2 in the absence of treatment within 4 weeks
- General or specific changes in the patient's condition render the patient unacceptable for further treatment in the judgment of the investigator,
- Patient decision to withdraw from treatment (partial consent) or from the study (full consent),
- Pregnancy during the course of the study
- Death

The date and reason for discontinuation must be documented. Every effort should be made to complete the appropriate assessments.

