## 4.2 Exclusion Criteria

- \_\_\_\_ 4.2.1 Patients with the presence of an active infection, abscess or fistula
- \_\_\_\_ 4.2.2 Known leptomeningeal disease or CNS midline shifts.
- \_\_\_\_ 4.2.3 Any evidence of severe or uncontrolled systemic disease such as clinically significant cardiovascular, pulmonary, hepatic, renal or metabolic disease.

- \_\_\_\_\_ 4.2.4 Severe conduction abnormality including significant QTc prolongation >450ms.
- \_\_\_\_\_ 4.2.5 Patients with grade 3/4 peripheral neuropathy.
- \_\_\_\_\_ 4.2.6 Patients with pacemaker or an ICD devices.
- \_\_\_\_\_ 4.2.7 Previous treatment with eribulin mesylate.

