#### **Recommended dose delays**

##### **Do not administer eribulin mesylate on Day 1 or Day 8 for any of the following:**

ANC < 1,000/mm^3

Platelets < 75,000/mm^3

Grade 3 or 4 non-hematological toxicities.

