#### **The Day 8 dose may be delayed for a maximum of 1 week.**

If toxicities do not resolve or improve to  $\leq$  Grade 2 severity by Day 15, omit the dose.

If toxicities resolve or improve to  $\leq$  Grade 2 severity by Day 15, administer eribulin mesylate at a reduced dose and initiate the next cycle no sooner than 2 weeks later.

Recommended dose reductions: If a dose has been delayed for toxicity and toxicities have recovered to Grade 2 severity or less, resume eribulin mesylate at a reduced dose as set out in Table 1. Do not re-escalate Eribulin dose after it has been reduced.

Table 2: Recommended Dose Reductions Event Description	Recommended Eribulin Dose
Permanently reduce the 1.4 mg/m^2 eribulin mesylate dose for any of the following:	1.1 mg/m 
ANC <500/mm  for >7 days	
ANC <1,000 /mm  with fever or infection	
Platelets <25,000/mm 	
Platelets <50,000/mm  requiring transfusion	
Non-hematologic Grade 3 or 4 toxicities	
Omission or delay of Day 8 Eribulin dose in previous cycle for toxicity	
Occurrence of any event requiring permanent dose reduction while receiving 1.1 mg/m^2	0.7 mg/m 
Occurrence of any event requiring permanent dose reduction while receiving 0.7 mg/m^2	Discontinue eribulin mesylate

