### **8.1.3 Peripheral Neuropathy**

- Grade 3 peripheral neuropathy occurred in 8% of patients, and Grade 4 in 0.4% of patients who received eribulin. Delay administration of eribulin until resolution to Grade 2 or less.
- Neuropathy lasting more than 1 year occurred in 5% of patients. Twenty-two percent of patients developed a new or worsening neuropathy that had not recovered within a median follow-up duration of 269 days (range 25-662 days)
- Peripheral neuropathy (5%) was the most common adverse reaction resulting in discontinuation

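### For a patient with baseline below Grade 2 who is off eribulin at Grade 2 toxicity at or after 4 weeks, Section 3.4 says stop while Sections 7.2 and 8.1.3 say resume

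*Combined protocol and SAP*

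**What the plan says.** Three sections deal with recovery from toxicity.

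- **Section 3.4 (Duration of Therapy)** lists, among the reasons for ending treatment, unacceptable treatment-related toxicity of "Grade 3 or 4 that fails to recover to baseline or < Grade 2 in the absence of treatment within 4 weeks".
- **Section 7.2 (Dose Modification)** withholds a Day 1 or Day 8 dose for "Grade 3 or 4 non-hematological toxicities", as well as for low neutrophil or platelet counts. Its restart rule is that once "toxicities have recovered to Grade 2 severity or less, resume eribulin mesylate at a reduced dose as set out in Table 1". On timing it says only that "The Day 8 dose may be delayed for a maximum of 1 week". If toxicity has come down to Grade 2 or lower by then, the instruction is to dose: "severity by Day 15, administer eribulin mesylate at a reduced dose and initiate the next cycle no sooner than 2 weeks later". It gives no maximum for a delayed Day 1 dose.
- **Section 8.1.3 (Peripheral Neuropathy)** says "Delay administration of eribulin until resolution to Grade 2 or less", with no time limit.

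Section 3.4 does not mention the restart rule. Sections 7.2 and 8.1.3 do not mention the 4-week limit. No section says which takes precedence. On entry status, Section 4.2 excludes only "Patients with grade 3/4 peripheral neuropathy", so a patient may enter with Grade 2 neuropathy.

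**The concern.** The rules differ in two respects. On grade, 3.4 requires recovery to baseline or below Grade 2, while 7.2 and 8.1.3 accept Grade 2 itself. On time, 3.4 allows 4 weeks off treatment, while 7.2 and 8.1.3 have no overall limit. Where both sets apply to the same patient, one site could discontinue her and another could restart her at a reduced dose, each following the protocol.

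The main stake is safety and consistent conduct: dosing after a severe toxicity would depend on which page the site consulted. A secondary stake is the trial data. The calendar in Section 10.2 ties brain MRI to being on eribulin, and Sections 3.6 and 13.0 (Evaluability) require the week-12 MRI. Who remains on drug could therefore influence who is scanned.

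**Working it through.** The plan states no figure on this point, so there is none to reproduce. The check is to apply the rules to each course a Grade 3-4 non-hematological toxicity can take once dosing is held.

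1. **Baseline Grade 0-1, falls to Grade 2 before 4 weeks.** Sections 7.2 and 8.1.3 allow a restart. Section 3.4 has not triggered, and its condition of no treatment lapses when dosing resumes. There is no opposite instruction, but the patient is back on drug without meeting the 3.4 recovery standard.
2. **Baseline Grade 0-1, off drug and at Grade 2 when 4 weeks are reached, or first at Grade 2 after that.** The patient is neither at baseline nor below Grade 2 within the limit, so 3.4 ends treatment. She is at Grade 2 or lower, so 7.2 and 8.1.3 resume it. This is a direct contradiction.
3. **Baseline Grade 2, back to Grade 2 within 4 weeks.** Recovery to baseline satisfies 3.4, and 7.2 and 8.1.3 also allow a restart. No conflict.
4. **Still Grade 3-4 at 4 weeks.** Section 3.4 stops; 7.2 and 8.1.3 still withhold. No opposite instruction on dosing at that point.
5. **Down to Grade 0-1 within 4 weeks.** All three sections allow treatment. No conflict.

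Only course 2 gives opposite instructions. Course 1 shows that the thresholds are not aligned even where the actions do not collide.

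**Sensitivity to the inequality sign.** Suppose the less-than sign in 3.4 were meant as less-than-or-equal. A patient at Grade 2 by 4 weeks would then satisfy 3.4, and the grade mismatch would vanish. A patient with baseline below Grade 2 who first reaches Grade 2 in week 5 would still be stopped by 3.4 and resumed by 7.2 and 8.1.3. The time-limit mismatch does not depend on the sign.

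**Size.** The only relevant rate is in Section 8.1.3: Grade 3 neuropathy in 8% and Grade 4 in 0.4%. The sum is 8% + 0.4% = 8.4%, and 20 x 0.084 = 1.68, about 1.7 patients. These are patients who could enter courses 1 to 5 through neuropathy, not patients in course 2. The share at Grade 2 after 4 weeks off drug is not given, nor is a corresponding rate for other toxicities.

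**Table reference.** The restart sentence in 7.2 sends the reader to Table 1. Table 1, in Section 6.1, holds the starting regimen. The reduced doses are in Table 2, in Section 7.2.

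**The case against.** The strongest reply is that the sections do different jobs. Section 7.2 says when a held dose may restart, and 3.4 is a permanent stop that applies only after 4 weeks without treatment. On that view 3.4 is simply the outer limit on 7.2. This is a reasonable reading and it disposes of most courses. It does not settle course 2, because no section states that 3.4 limits 7.2 or 8.1.3.

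The baseline alternative in 3.4 also stands: it removes the conflict for patients who entered with Grade 2 toxicity and return to it in time.

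A third reply is that the grade difference rests on one sign, and the document is loose with signs. In Section 11.1.4 the text on CNS response uses strict inequalities for the 50% and 25% limits, while the table in 11.1.4.1 uses non-strict ones. The text was also read from PDF. This limits confidence in the grade mismatch, although 7.2 keeps its less-than-or-equal signs. It does not remove the time-limit mismatch.

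The table reference is a clerical slip. Table 2 follows the sentence directly, so a wrong dose from this cause is unlikely.

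Stronger readings are tempting but are not supported:

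- *Every patient who improves to Grade 2 gets opposite instructions.* Courses 1 and 3 show otherwise.
- *About 4.4 of 20 patients are affected (20 x 0.22).* The 22% in Section 8.1.3 is new or worsening neuropathy with no grade stated, whereas 3.4 concerns Grade 3-4 toxicity. It cannot be used as a count.
- *Each patient affected moves the primary proportion by 5 points (1/20).* A replaced patient leaves the denominator at 20. The proportion moves by 5 points only if the replacement's outcome differs, and otherwise not at all.
- *The rule a site applies decides whether the patient is counted.* Evaluability needs the week-12 MRI, not continued dosing. Section 11.1.4 schedules MRI until progression, and 3.4 asks sites to try to complete assessments at discontinuation. The calendar footnote points the other way, so a link exists, but it is indirect.

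**Conclusion.** The protocol is wrong as written: it contains an internal contradiction, confined to course 2. The threshold in 3.4 can also be bypassed by an earlier restart at Grade 2.

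The number of patients concerned cannot be computed from the documents. The figure of about 1.7 of 20 is the expected neuropathy pool at risk. It assumes that the rates quoted in 8.1.3 carry over to this population, and other Grade 3-4 toxicities could add to the pool. No numerical effect on the 3-month CNS PFS proportion can be claimed.

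The grade part of the finding assumes that the sign in 3.4 is as printed; the time part does not. The case for correcting the text rests on safety and uniform conduct, not on a demonstrated bias. The documents do not show which of the rules was intended, and this review takes no view on that.

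**What to change.** Reconcile Sections 3.4, 7.2 and 8.1.3. State which rule governs resumption after a hold and which governs permanent discontinuation, and cross-refer between them so that course 2 has one answer. The text should also say whether the 4-week limit applies to a delayed Day 1 dose and to the neuropathy delay. The recovery grades and time limits, and whether restart and stopping should share them, are for the sponsor's clinical team to decide. In the same edit, change the table reference in the 7.2 restart sentence from Table 1 to Table 2.

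The cost is a wording amendment. The sample size, the endpoint definition and the analysis are unchanged.

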### **3.5 Duration of Follow Up:**

**30-Day Follow-Up:** Patients will be followed *for toxicity* for 30 days after treatment has been discontinued or until death, whichever occurs first.

**Long term Follow-Up:** Patients will be followed *for survival* every 3 months until death after discontinuation of study medications.

The clinical course of each event will be followed until resolution, stabilization, or until it has been determined that the study treatment or participation is not the cause.

Serious adverse events that are still ongoing at the end of the study period will necessitate follow-up to determine the final outcome. Any serious adverse event that occurs after the study period and is considered to be possibly related to the study treatment or study participation will be recorded and reported immediately.

### **3.6 Replacement of Subjects**

Subjects who do not obtain the two MRI scans (baseline and 12 weeks) will be considered not evaluable for response and will be replaced.

